6.4.3 Post Treatment and Pinch Test

- [REDACTED] forceps will be used to “pinch” the [REDACTED] conjunctiva of the study eye at the following timepoints. Details on the pinching method will be provided separately:
 - **20 seconds following complete dose administration** (second drop of IMP)
 - **40 seconds following dose administration**
 - **60 seconds following dose administration**
 - **5 minutes following dose administration**
- Immediately following EACH pinch test, subjects will be asked “Was that painful” “Yes” or “NO.” It should be explained to subjects that the feeling of pressure is NOT to be judged as pain. [REDACTED]
[REDACTED].

All subjects are pinched at 20, 40, 60 seconds and 5 minutes post dose. If the subject feels no pain at 5 minutes, the subject will be considered “anesthetized.” Pinching of anesthetized subjects will continue at 10 minutes and EVERY FIVE MINUTES for up to 30 minutes or until pain resumes. Once pain resumes, pinching is stopped.

If the subject experiences pain at 5 minutes, pinching will be concluded and this subject will be considered to NOT have reached anesthesia at 5 minutes.

Within 15-60 minutes after the last pinch test, the following examinations will be performed

- BCVA
- Perform slit lamp biomicroscopy and external eye exam
- Assess for adverse events
- Schedule Follow-up Phone Call between Day 2-5 (1-4 days following dosing).

Windows: Times will be measured to the nearest minute with the exception of the 20, 40 and 60 second time points. Those should be recorded to the second. Times up to 5 minutes post 2nd instillation should be followed. Investigators are allowed a window of \pm 1 minute at the 10 minute time point, and \pm 2 minutes at subsequent time points.

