### **2.6.2 Secondary efficacy measure**

The secondary efficacy endpoints include the following:

- Time in minutes to no pain within 5 minutes post application of the dose defined as post the 2nd drop of the dose. Once a subject achieves no pain or anesthetic effect, the time to the onset of anesthetic effect will be calculated as the time interval in number of minutes between the time of dose application completion and the time point when the first observation of no pain is recorded. All timepoints post dose will be converted to minutes so the 20, 40 and 60 second timepoints will be 0.33, 0.67 and 1.0 minutes, respectively. For those subjects who drop out after dose application without achieving anesthesia or who do not achieve the anesthetic effect within 5 minutes post dose, the time to the anesthetic effect will be considered being censored at the last assessment of pinch test or at 5 minutes (censored time point), whichever occurs earlier.
- Duration in minutes from the onset of anesthetic effect to the time point when pinch pain resumes. For those subjects who have achieved an anesthetic effect post dose, the duration of anesthetic effect is calculated by subtracting the anesthetic effect onset time from the time of the first observation of pinch pain return. For those subjects who did not achieve an anesthetic effect post dose, this duration is not applicable and will be set to missing.

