### **2.8 Handling of Missing, Incomplete, and Repeat Data**

For efficacy parameters, missing or invalid data for pinch pain assessment will be assessed for each assessment time point post dose. Missing values that occur either within 5 minutes (inclusive) post dose or after 5 minutes post dose, due to either invalid data or early termination, will be imputed with the method of last-observation-carried-forward (LOCF) for the planned assessment time points on Day 1.

For safety parameters, missing or invalid data will be treated as missing for the corresponding assessment of a visit.

All data records are identified by study visit and/or assessment time point. Should repeated data records exist within a study visit and/or assessment time point, the first valid data record will be utilized for any statistical analyses of the corresponding study visit and/or assessment time point. All existing data records including the repeat data records in the study database will be presented in data listings and CRF data tabulations.

Any resultant incomplete or missing data of either efficacy or safety parameters will be treated as missing in the statistical analyses involving these parameters.

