#### Onset of anesthetic effects

The secondary endpoint of the onset of anesthetic effect in minutes from time of dose application completion to no pain within 5 minutes post dose is defined in Section 2.6.2. This endpoint will be compared for between-group differences, using a 2-way ANOVA model with treatment (the effect of interest) and study eye side as the effects. The study-eye-side effect is used as a blocking factor in the model to control the potential treatment differences among the study eye sides. For the accuracy and appropriateness of the analysis, those subjects who are censored on (or not achieving) the onset of anesthetic effect will be excluded from statistical analysis.

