### Duration of anesthetic effects

The secondary endpoint of the duration of anesthetic effect in minutes from the onset of anesthetic effect to the time point when pinch pain resumes is defined in Section 2.6.2. This endpoint will be compared for between-group differences, using a 2-way ANOVA model with treatment (the effect of interest) and study eye side as the effects. The study-eye-side effect is used as a blocking factor in the model to control the potential treatment differences among the sites.

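### SAP 2.6.2 gives no calculable duration to an achiever still pain-free at the last pinch, and the text points to leaving that subject out of the duration ANOVA

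*SAP*

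**What the plan says.** Protocol section 2 lists the mean duration of anesthetic effect as a secondary endpoint.

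- **Definition.** SAP 2.6.2 has an achiever's duration "calculated by subtracting the anesthetic effect onset time from the time of the first observation of pinch pain return". Its only other rule on duration concerns non-achievers: "For those subjects who did not achieve an anesthetic effect post dose, this duration is not applicable and will be set to missing".
- **Follow-up.** Protocol 6.4.3 continues pinching of subjects with no pain at 5 minutes at 10 minutes and then "EVERY FIVE MINUTES for up to 30 minutes or until pain resumes". SAP 2.6.1 says the same. On timing, the protocol adds: "Investigators are allowed a window of" 1 minute either side at the 10-minute pinch and 2 minutes either side afterwards.
- **Analysis.** SAP 2.9.2 on duration: "This endpoint will be compared for between-group differences, using a 2-way ANOVA model with treatment (the effect of interest) and study eye side" as effects. It does not mention subjects without a pain return.
- **Onset, for contrast.** For a subject who does not become numb, SAP 2.6.2 states that "the time to the anesthetic effect will be considered being censored at the last assessment of pinch test or at 5 minutes", whichever is earlier. SAP 2.9.2 then says that "those subjects who are censored on (or not achieving) the onset of anesthetic effect will be excluded from statistical analysis". Duration has no counterpart to either sentence.
- **Missing data.** Protocol 9.5 and SAP 2.8 apply last observation carried forward (LOCF) to the Day 1 pinch assessments. SAP 2.8 ends: "Any resultant incomplete or missing data of either efficacy or safety parameters will be treated as missing in the statistical analyses" that involve them.

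**The concern.** The definition needs an event that follow-up may end too early to record. The subjects it fails to cover are those in whom the anesthetic lasted longest. Leaving them out selects on the outcome itself: at nominal times, a return found at the 30-minute pinch counts, and one that would have come after it does not.

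At stake is the estimate for a named secondary endpoint, with inferential statistics planned in Table 2.4.1. The loss would show in that table's n and in Listing 6, but only once the data are in hand, when a choice of rule is no longer prespecified.

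**Working it through.** **1. Does any text supply the value?** The plan states no figure for duration, so the check begins with the rules.

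- A subject pain-free at the 30-minute pinch has no missing pinch, so LOCF has nothing to fill.
- For a subject who leaves while numb, LOCF carries no pain forward to 30 minutes. That creates no return time.
- The missing-value rule in SAP 2.6.2 is for non-achievers only.
- What remains is the closing sentence of SAP 2.8, together with an ANOVA that cannot use a right-censored value. Together they lead to exclusion, by inference.

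At nominal times the longest calculable duration is 30 - 0.33 = 29.67 minutes, and that subject stays in the analysis. The same onset with no pain at 30 minutes means a duration above 29.67 minutes and no value.

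**2. Size in one arm.** Let q be the share of achievers still numb at 30 minutes, and R the mean recorded return time of the others. With a common onset, onset cancels:

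mean scored at the 30-minute pinch - mean with exclusion = q × (30 - R)

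R cannot exceed 30 at nominal times, so the difference is never negative. (If onsets vary, or pinches move within the windows, the inequality need not hold exactly.) With R = 20 assumed, the difference is 0 at q = 0, 0.5 minutes at 5%, 2.0 at 20% and 3.5 at 35%.

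**3. Illustration with assumed durations.** Onset is at 1 minute, durations are Weibull with shape 2, subjects are pain-free at 5 minutes (duration above 4), and return is recorded at the next pinch. Recorded durations are therefore 9, 14, 19, 24 or 29 minutes.

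For a nominal mean of 20, the probabilities of those five values are 0.1198, 0.1779, 0.1943, 0.1749 and 0.1351, and 0.1979 are still numb.

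- Excluded: (9×0.1198 + 14×0.1779 + 19×0.1943 + 24×0.1749 + 29×0.1351) / 0.8021 = 19.2
- Scored at 30 minutes: 0.8021 × 19.17 + 0.1979 × 29 = 21.1

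| Nominal mean | Still numb | Excluded | Scored at 30 min | Continuous mean, achievers |
|---|---|---|---|---|
| 10 | 0.2% | 13.6 | 13.6 | 11.0 |
| 15 | 5.6% | 17.2 | 17.9 | 15.7 |
| 20 | 19.8% | 19.2 | 21.1 | 20.6 |
| 25 | 35.5% | 20.2 | 23.3 | 25.5 |

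Exponential durations give, for mean 10, 8.2% numb and 14.5 against 15.7; for mean 15, 18.9% numb and 15.8 against 18.3.

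Against continuous duration, the excluded mean is too high at first, because return is recorded only at the next 5-minute pinch. It drops below once about 13% are numb (about 10% for exponential durations).

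**4. Treatment difference.** SAP 2.5 plans 60 per arm, 15% response on placebo and a 25-point difference, so expected 5-minute responders are 60 × 0.40 = 24 and 60 × 0.15 = 9. Assume observed means of 19 and 14, a difference of 5.0 with exclusion, and score numb subjects at 29.

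- 5 of 24 and 0 of 9 numb: (19×19 + 5×29)/24 - 14 = 21.1 - 14 = 7.1
- 2 of 24 and 1 of 9 numb: (22×19 + 2×29)/24 - (8×14 + 29)/9 = 19.8 - 15.7 = 4.2

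Exclusion can therefore shrink or enlarge the difference. In 200,000 simulated trials of 24 against 9, it was smaller than with 30-minute scoring in 99% of trials and larger in 1% (shape 2, means 20 and 10); 85% and 15% (shape 2, 20 and 15); 78% and 21% (exponential, 15 and 10).

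**The case against.** The strongest reply is that the text is not really open. Duration requires an observed return, a numb subject has none, SAP 2.8 treats what is left as missing, and the sponsor openly excludes censored subjects for onset. On that view exclusion is a choice that merely lacks its sentence, and scoring at 30 minutes is a rule the SAP does not contain. The first part largely stands: the two treatments are not equally supported, and the 30-minute score serves here only as a yardstick. It does not rescue the method, because exclusion here removes the best responders.

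The reply is also right that every non-zero figure rests on assumed durations, that Table 2.4.1 would reveal the loss, and that one sentence plus a count would close the gap while keeping a mean.

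A reader might go further than the documents allow in three ways:

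- That recorded durations are discarded. They are not; what leaves is right-censored follow-up that never had a recorded duration.
- That the result is biased against AG-920. That is likely if AG-920 lasts longer, but the second case in step 4 goes the other way.
- That the SAP explicitly orders exclusion for duration. It does so only for onset. The table shells are not in the documents, so a rule there cannot be ruled out.

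**Conclusion.** The point holds in limited form. The plan gives no usable duration to an achiever without an observed pain return, and its text, read together, points to exclusion. Following it would give a mean at or below the 30-minute-scored mean in each arm, given nominal pinch times and a common onset. The shortfall is nil if nobody outlasts 30 minutes and about 1.9 minutes (21.1 - 19.2) if about 20% do, under the assumed shape 2 Weibull. The real share is not in the documents.

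The direction for the treatment difference is not certain. The comparison is limited to achievers and so is not a randomised one under any method. The primary endpoint and the superiority claim are untouched. The change should be made before unmasking, but it does not threaten the trial's main conclusion.

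**What to change.** - **SAP 2.6.2:** right-censor duration at the last observed no-pain pinch for achievers without a pain return, whether still numb at 30 minutes or gone while numb. Do not apply LOCF to this endpoint.
- **SAP 2.9.2:** replace the ANOVA on observed returns with Kaplan-Meier estimates per arm (median with 95% CI, or a restricted mean with a stated horizon), and report the number censored per arm. Present the comparison between arms as descriptive; a log-rank test is optional.
- **Horizon, if a restricted mean is used:** a last pinch at 28 minutes is within the window, so only 28 - 5 = 23 minutes from a 5-minute onset is assured. A 25-minute horizon recovers part of the lost difference: for shape 2 means of 20 against 10, it is 5.6 with exclusion, 6.2 at 25 minutes and 7.5 with 30-minute scoring.
- **Separately, reconcile SAP 2.6.1 and 2.6.2.** A subject numb at 20 seconds and in pain at 60 seconds and at 5 minutes has, by 2.6.2, an onset and a duration of 1.0 - 0.33 = 0.67 minutes, while 2.6.1 treats that subject as not having reached anesthesia. The counts of 24 and 9, and the model above, take the 2.6.1 view.

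**Cost.** No new data and no change to the pinch schedule. The median falls on the 5-minute grid, is imprecise with about 9 placebo achievers, and cannot be estimated if half or more of an arm is still numb. Moving away from the mean in Protocol section 2, and from LOCF in Protocol 9.5 and SAP 2.8, needs an amendment or a justified deviation under Protocol 9.6.

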### **2.6.1 Primary efficacy measure**

The primary efficacy endpoint for this study is the proportion of subjects with anesthetic response defined as no pain at 5 minutes post application of the dose. Pain is assessed using conjunctival pinch procedure. Dosing of the study medication and conjunctival pinch procedure will be performed by the study staff.

To assess the anesthetic effect of the study medication, all subjects will be pinched at 20, 40, 60 seconds and 5 minutes post dose application. If the subject feels no pain at 5 minutes, the subject will be considered "anesthetized." Pinching of anesthetized subjects will resume at 10 minutes and pinching will continue every five minutes for up to 30 minutes or until pain resumes. If the subject experiences pain 5 minutes post dose application, pinching will be concluded and this subject will be considered to NOT have reached anesthesia.

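### SAP 2.6.2, read literally, derives onset and duration without reference to the 5-minute pinch that defines anesthesia, so non-anesthetized subjects can get values and some anesthetized subjects get durations of 20 or 40 seconds

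*SAP*

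**What the plan says.** **Testing scheme.** Protocol 6.4.3: "All subjects are pinched at 20, 40, 60 seconds and 5 minutes post dose". Only subjects pain-free at 5 minutes go on to 10 minutes and then every five minutes, until pain resumes or 30 minutes is reached.

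**Who is anesthetized.** Protocol 6.4.3 and SAP 2.6.1 settle this by the 5-minute pinch alone. For a subject in pain then, pinching ends and, in SAP 2.6.1, "this subject will be considered to NOT have reached anesthesia".

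**Onset.** SAP 2.6.2 says "Once a subject achieves no pain or anesthetic effect, the time to the onset of anesthetic effect will be calculated", running from completion of dosing to "the time point when the first observation of no pain is recorded". Censoring applies to drop-outs without anesthesia and to those "who do not achieve the anesthetic effect within 5 minutes post dose". The wording is within, not at, 5 minutes.

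**Duration.** SAP 2.6.2 computes it by "subtracting the anesthetic effect onset time from the time of the first observation of pinch pain return". The only exclusion is: "For those subjects who did not achieve an anesthetic effect post dose, this duration is not applicable and will be set to missing".

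**Analysis.** SAP 2.9.2 compares both endpoints by two-way ANOVA. It drops from the onset analysis those censored or not achieving onset. It does not restrict either analysis to subjects pain-free at 5 minutes.

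**The concern.** Four early pinches are given whatever the earlier answers, so a subject can report no pain, then pain, then no pain again. The SAP does not say what to do with that sequence, and its two definitions then disagree. SAP 2.6.1 looks only at 5 minutes. SAP 2.6.2 looks at the first no-pain answer and the first pain answer after it, and treats no pain and anesthetic effect as the same event.

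Two results follow from the literal text. A subject whom the trial declares not anesthetized can carry an onset and a duration into both ANOVAs. A subject whom the trial declares anesthetized can have a duration of seconds because of one painful answer at 40 or 60 seconds.

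At stake are the two secondary efficacy objectives: how quickly one dose anesthetizes the eye, and for how long. The reported means could mix isolated no-pain answers with anesthesia as the trial defines it, in both arms. Two programmers could also derive different datasets from the same SAP.

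**Working it through.** **1. The plan's own figure.** SAP 2.5 gives 60 per group, 15% placebo, a 25-point difference (so 40% active), two-sided 0.05, uncorrected chi-square, 88% power. The average rate is (0.15 + 0.40)/2 = 0.275.

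- Standard error under the null: √(2 × 0.275 × 0.725 / 60) = 0.0815
- Standard error under the alternative: √((0.15 × 0.85 + 0.40 × 0.60)/60) = 0.0783
- Power: Φ[(0.25 − 1.96 × 0.0815)/0.0783] = Φ(1.153) = 0.8755

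This agrees with 88%. The figure is not in dispute. It confirms the rates used as assumptions in step 4.

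**2. SAP 2.6.2 applied to every early pattern.** N is no pain and P is pain, in the order 20 s, 40 s, 60 s, 5 min. For the early times SAP 2.6.2 states that "the 20, 40 and 60 second timepoints will be 0.33, 0.67 and 1.0 minutes, respectively". Duration is the time of the first P after the first N, minus the time of that N.

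Pain at 5 minutes (declared not anesthetized), 8 patterns:

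| Pattern | Onset (min) | Duration (min) |
|---|---|---|
| NPPP | 0.33 | 0.33 |
| NPNP | 0.33 | 0.33 |
| NNPP | 0.33 | 0.67 |
| NNNP | 0.33 | 4.67 |
| PNPP | 0.67 | 0.33 |
| PNNP | 0.67 | 4.33 |
| PPNP | 1.0 | 4.00 |
| PPPP | censored | missing |

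Seven of the eight get both values.

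No pain at 5 minutes (declared anesthetized), 8 patterns:

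| Pattern | Onset (min) | Duration (min) |
|---|---|---|
| NPPN | 0.33 | 0.33 |
| NPNN | 0.33 | 0.33 |
| NNPN | 0.33 | 0.67 |
| PNPN | 0.67 | 0.33 |
| NNNN, PNNN, PPNN, PPPN | 0.33, 0.67, 1.0, 5.0 | set by later pinches |

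Four of the eight get 20 or 40 seconds, whatever happens after 5 minutes.

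**3. One subject, three durations.** Take no pain at 20 s, pain at 40 s, no pain from 60 s through 15 min, pain at 20 min.

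- Literal SAP 2.6.2: 0.67 − 0.33, about 0.33 min (20 seconds)
- First no-pain to the pain that ends testing: 20 − 0.33 = 19.67 min, which spans a painful pinch
- Unbroken run containing 5 minutes: 20 − 1 = 19 min

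**4. How often.** The documents give no early-pinch rates and no within-subject correlation. As an illustration, assume the same no-pain rate p at all four pinches (0.15 placebo, 0.40 AG-920) and a beta-binomial model with correlation ρ. Let s = (1 − ρ)/ρ, a = ps, b = (1 − p)s.

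Early relapse among 5-minute responders (the four relapse patterns, divided by p) reduces to 2(a + 1)b / [(s + 1)(s + 2)], or 2p(1 − p) at ρ = 0. For AG-920:

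- ρ = 0: 2 × 0.40 × 0.60 = 0.48
- ρ = 0.8 (s = 0.25, a = 0.10, b = 0.15): 2 × 1.10 × 0.15 / (1.25 × 2.25) = 0.12
- ρ = 0.95 (s = 0.0526, a = 0.0211, b = 0.0316): 2 × 1.0211 × 0.0316 / (1.0526 × 2.0526) = 0.03
- ρ = 1: 0

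With 0.40 × 60 = 24 expected responders, that is about 12, 3, 1 and 0 subjects.

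The share with an onset despite pain at 5 minutes is 1 − Pr(PPPP) − p. At ρ = 0:

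- AG-920: 1 − 0.60⁴ − 0.40 = 0.470, about 28 of 60
- Placebo: 1 − 0.85⁴ − 0.15 = 0.328, about 20 of 60

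At ρ = 0.8, Pr(PPPP) = b(b + 1)(b + 2)(b + 3) / [s(s + 1)(s + 2)(s + 3)]. This is 0.511 for AG-920 and 0.801 for placebo, leaving about 5 and 3 of 60. At ρ = 1 both are 0.

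The model matters too. A first-order Markov chain with correlation 0.8 between successive pinches puts early relapse at 0.011 of the AG-920 arm, or 0.011/0.40, about 3% of responders. The beta-binomial gives 12% at the same nominal correlation.

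**The case against.** **Pain resumption has a context.** In Protocol 6.4.3 and SAP 2.6.1, pain resuming is the event that stops testing in an anesthetized subject after 5 minutes. Pain at 40 or 60 seconds stops nothing. If SAP 2.6.2 borrows that sense, the 20-second responder disappears. This reading is plausible and may be what was meant. But 2.6.2 does not state it, and its calculation sentence refers to the first observation of pain return. Even on this reading the start of the duration stays at the first isolated no-pain pinch (19.67 rather than 19 min in the example).

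**A programmer could import the 5-minute definition.** Setting duration to missing for subjects in pain at 5 minutes would agree with SAP 2.6.1. The SAP does not instruct it, and it would leave the four early-relapse patterns untouched.

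**First no-pain is the protocol's onset.** Protocol Section 2 names the endpoint as mean time to a no-pain score. A reader might infer that the SAP's onset rule is simply wrong. The documents do not support that: it follows the protocol's wording, and requiring a sustained response is partly a choice. This part of the objection stands.

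**The frequencies are model output.** This also stands. A reader might take 12% as a lower bound on early relapse. It is not, because the range runs to 0.

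**Conclusion.** The concern holds as a defect in a literal derivation rule. The pattern counts (7 of 8 and 4 of 8) follow from the text and the pinch schedule and need no assumption about rates. How many subjects are affected cannot be determined from the documents. The figures of 48%, 12%, 3% and 0 rest on a constant 40% no-pain rate at each pinch and on the assumed correlation.

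Two stronger readings fail. A reader might suppose that a relapsing 5-minute responder could be assigned up to 4.67 min. That is impossible: relapse before a pain-free 5-minute pinch can be seen only at 40 or 60 seconds, so the values are about 0.33 or 0.67 min. The longer values belong to subjects in pain at 5 minutes. A reader might also suppose that the trial's main result is at risk. The primary endpoint uses only the 5-minute status, so it and its power are unaffected. The point concerns onset and duration, and should be settled before unmasking.

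**What to change.** Amend SAP 2.6.2 and 2.9.2 before unmasking.

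- **Duration.** Compute it only for subjects pain-free at 5 minutes. Start at the first pinch of the unbroken no-pain run that contains the 5-minute pinch, and end at the first painful pinch after 5 minutes. Set it to missing for subjects in pain at 5 minutes.
- **Onset.** Report time to the sustained response among 5-minute responders alongside time to first no-pain, which is the protocol's literal endpoint. State in advance which is the main analysis.
- **Sensitivity.** Keep a table using the first-response derivation.

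The cost is SAP wording and a change of derivation; no new data are needed. The downsides are real. Fewer subjects carry values, and onset looks slower. Effects that wear off before 5 minutes leave the duration analysis. At nominal times no duration with an observed pain return can be below 10 − 5 = 5 min. The sensitivity table shows what is lost.
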